4. SUBJECT DISPOSITION

4.1. Subject Enrollment and Disposition

A summary of subject enrollment will be provided by treatment group for each country, investigator and overall. The summary will present the number and percentage of patients enrolled. For each column, the denominator for the percentage calculation will be the total number of patients analyzed for that column.

A similar enrollment table will be provided by randomization stratum. The denominator for the percentage of patients in the stratum will be the total number of enrolled patients. If there are discrepancies in the value used for stratification assignment between the IXRS and the clinical database, the value collected in the clinical database will be used for the summary. A listing of patients with discrepancies in the value used for stratification assignment between the IXRS and the IXRS and the clinical database at the time of data finalization will be provided.

The randomization schedule used for the study will be provided as an appendix to the CSR.

A summary of subject disposition will be provided by treatment group. This summary will present the number of patients screened and the number of patients who met all eligibility criteria but were not randomized with reasons patients not randomized in total; and the number of patients in each of the categories listed below by treatment group:

- ITT Analysis Set
- Safety Analysis Set
- Continuing study treatment (magrolimab/placebo, azacitidine)
- Discontinued study treatment (magrolimab/placebo, azacitidine) with reasons for discontinuation
- On-going in study (including long-term follow-up and survival follow-up)
- Discontinued study with reasons for discontinuation

For the status of study drug and study completion and reasons for discontinuation, the number and percentage of patients in each category will be provided. The denominator for the percentage calculation will be the total number of patients in the ITT Analysis Set corresponding to that column. In addition, a CONSORT flow diagram will be provided to depict the disposition.

A by-subject listing with reasons for study drug or study discontinuation will be provided by subject identification (ID) number in ascending order to support the above summary table.

4.2. Extent of Study Drug Exposure

Extent of exposure to study drug will be examined by assessing the total duration of exposure to study drug and relative dose intensity. Each summary statistic will be calculated for magrolimab/placebo, and azacitidine separately. No formal statistical testing between treatment group is planned.

4.2.1. Duration of Exposure to Study Drug

Total duration of exposure to each study drug (magrolimab/placebo, and azacitidine) will be defined for a subject as last dosing date minus first dosing date plus 1 day, regardless of any temporary interruptions in study drug administration, and will be expressed in weeks using up to 1 decimal place (eg, 4.5 weeks).

The total duration of exposure to each study drug will be summarized using descriptive statistics for continuous variables, as well as using the number (i.e., cumulative counts) and percentage of patients exposed for at least the following time periods: 1 day, 4 weeks, 8 weeks, 12 weeks, 16 weeks, 20 weeks, and 24 weeks, etc.

For azacitidine, the number of cycles patients are exposed will be summarized using descriptive statistics, and the number and percentage of patients who received at least 1, 2 ..., 6 cycles will be presented.

The number and percentage of patients who have dose reduction for azacitidine or delay for each drug and the reasons will be summarized.

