6.7. Dose Modification and Delays

6.7.1. Magrolimab/Placebo

6.7.1.1. Dose Modifications

In clinical experience with magrolimab, no significant dose-dependent toxicities have been identified. Therefore, in general, dose modifications to magrolimab/placebo should not be made. In rare circumstances, the dose of magrolimab/placebo may be reduced for \geq Grade 3 AEs that are deemed clearly related to magrolimab/placebo and not azacitidine and that do not resolve to \leq Grade 2 or baseline value within 14 days of onset. However, dose delay of magrolimab/placebo should occur first, and if the AE does not resolve, then a magrolimab/placebo dose reduction can be considered. Please notify the blinded Medical Monitor of any planned dose delays. If a magrolimab/placebo dose reduction is considered, an initial 33% dose reduction (from 30 to 20 mg/kg) should be done first. If no improvement is observed within at least 28 days, further magrolimab/placebo dose reductions from 20 to 15 mg/kg may be warranted. For persistent bone marrow hypocellularity or peripheral cytopenias (where both azacitidine and magrolimab/placebo may have a contribution), the dose of azacitidine should be reduced (see Section 6.7.2.2). Participants can re-escalate to higher doses of magrolimab/placebo up to the original 30 mg/kg dose if AEs improve, after discussion with the Sponsor's Medical Monitor.

For dose modification for $> 10\%$ change in body weight, see Section 6.4.

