7.1.6.1. Summaries of AE incidence in Combined Severity Grade Subsets

A brief, high-level summary of the number and percentage of patients who experienced at least 1 TEAE in the categories described below will be provided by treatment group.

The number and percentage of patients who experienced at least 1 TEAE will be provided and summarized by SOC, PT, and treatment group.

- TEAEs
- TEAEs with Grade 3 or higher
- TE treatment-related AEs for any study drug and for each study drug
- TE treatment-related AEs with Grade 3 or higher for any study drug and for each study drug
- TE SAEs
- TE treatment-related SAEs for any study drug and for each study drug
- TEAEs leading to dose reduction of azacitidine
- TEAEs leading to discontinuation of any study drug and for each study drug
- TEAEs leading to death

Multiple events will be counted only once per subject in each summary. Adverse events will be summarized and listed first in alphabetic order of SOC and then by PT in descending order of frequencies in magrolimab + azacitidine treatment arm within each SOC. For summaries by severity, the most severe grade will be used for those AEs that occurred more than once in a given subject during the study.

In addition to the above summary tables, all TEAEs, TEAEs of Grade 3 or higher, TE SAEs and TEAEs leading to death will be summarized by PT only in descending order of frequencies in magrolimab + azacitidine treatment arm.

In addition, data listings will be provided for the following:

- All AEs, indicating whether the event is treatment emergent
- All SAEs
- All Deaths
- All SAEs leading to death
- All AEs with severity of Grade 3 or higher
- All AEs leading to discontinuation of study drug
- All AEs leading to dose reduction of azacitidine
- TEAEs leading to dose delay or interruption of study drug

A summary (number and percentage of patients) of deaths will be provided by treatment group. Summary will include the following categories:

- All deaths
- Deaths within 30 days of the first dosing of study drug
- Deaths within 30 days of the last dosing of study drug
- Deaths within 60 days of the first dosing of study drug
- Deaths within 70 days of the last dosing of study drug
- Deaths beyond 30 days of the last dosing of study drug
- Deaths beyond 70 days of the last dosing of study drug

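### The SAP leaves magrolimab/placebo out of every dose-reduction output and plans no by-arm SOC/PT table of the adverse events that led to holding it

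*SAP*

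**What the plan says.** SAP 4.2.1 ends its exposure summaries with this rule: "The number and percentage of patients who have dose reduction for azacitidine or delay for each drug and the reasons will be summarized". Reduction is tied to azacitidine; delay covers each drug.

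SAP 7.1.6.1 first lists categories to be tabulated: "The number and percentage of patients who experienced at least 1 TEAE will be provided and summarized by SOC, PT, and treatment group". The reduction category there is "TEAEs leading to dose reduction of azacitidine". The discontinuation category in the same list is wider: "TEAEs leading to discontinuation of any study drug and for each study drug".

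The section then turns to listings ("In addition, data listings will be provided for the following"). Two of them matter here: "All AEs leading to dose reduction of azacitidine" and "TEAEs leading to dose delay or interruption of study drug". The second appears only as a listing, with no matching table, and it is not split by drug.

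Protocol 6.7.1.1 says magrolimab/placebo should generally not be modified. It does allow reduction, in rare circumstances, for Grade 3 or higher events clearly related to magrolimab/placebo that have not resolved within 14 days. Delay is to be tried first; if reduction is then considered, "an initial 33% dose reduction (from 30 to 20 mg/kg) should be done first", with a possible further step to 15 mg/kg. Protocol 6.7.1.2 permits delay for adverse events under stated conditions.

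**The concern.** Safety and tolerability of the combination is a secondary objective in both documents. Magrolimab is the added agent and is compared with a blinded placebo, so what was done to magrolimab/placebo because of adverse events, by arm, is a direct measure of tolerability. The SAP provides that measure in its adverse event tables for discontinuation, but not for reduction or delay.

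At stake is the completeness of the safety report. If the SAP is followed as written, a reader could not see how many participants in each arm had magrolimab/placebo reduced, or for which events. The reader would see how many had it delayed and why, but not the SOC/PT pattern of the events behind those delays. Delays also have some bearing on efficacy, since Protocol 6.7.1.2 says that two-weekly dosing without significant delay is important for the best result.

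**Working it through.** The plan gives no figure to reproduce. The check sets each dose action against each planned output. Sources are SAP 4.1 (disposition), 4.2.1 (exposure), 4.2.2 (relative dose intensity) and 7.1.6.1 (adverse events), and Protocol 6.7.1 and 8.6.2.

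| Dose action | Count with reasons (SAP 4.1 or 4.2.1) | TEAE table by SOC, PT and arm (SAP 7.1.6.1) | Dedicated AE listing (SAP 7.1.6.1) |
|---|---|---|---|
| Azacitidine reduction | Yes | Yes | Yes |
| Magrolimab/placebo reduction | No | No | No |
| Azacitidine delay | Yes | No | Yes, not split by drug |
| Magrolimab/placebo delay | Yes | No | Yes, not split by drug |
| Discontinuation, each drug | Yes (4.1) | Yes | Yes |

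Step 1, reductions. The magrolimab/placebo reduction row has 0 of 3 outputs and the azacitidine row has 3 of 3. Discontinuation and treatment-related events are both reported for any drug and for each drug, so the SAP uses per-drug reporting elsewhere in the same list.

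Step 2, delays. The count with reasons exists for both drugs, and SAP 4.2 says the exposure statistics are computed separately for each. What is missing is the by-arm SOC/PT table. A secondary point is that 4.2.1 does not itself state that the summary is by treatment group, though that is the natural reading.

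Step 3, does the protocol fill the gap? Protocol 8.6.2 names only events resulting in withdrawal from treatment. It adds nothing on reduction or delay.

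Step 4, does relative dose intensity fill it? Under SAP 4.2.2 it is dose received divided by dose expected. As an illustration, take three maintenance infusions at 30 mg/kg, so that 3 × 30 = 90 mg/kg is expected:

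- All three given at the reduced 20 mg/kg: 3 × 20 = 60, and 60/90 = 66.7%.
- Two given at 30 mg/kg and one missed: 2 × 30 = 60, and 60/90 = 66.7%.

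Both fall in the example category below 75%. The measure cannot tell a reduction from a missed dose. Nor can it tell toxicity from the other reasons for holding a dose that the protocol foresees: surgery (Table 10), a high white cell count (6.7.1.2) or COVID-19 (Appendix H). It names no event.

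**The case against.** The strongest reply is that the SAP fits the protocol. Azacitidine has a multi-step reduction scheme. Magrolimab/placebo is generally not to be modified, and its reduction is described as rare. Counting reductions for the drug that is routinely reduced, and delays for both, is a reasoned choice. Protocol 8.6.2 asks for less than the SAP delivers, so no requirement is breached.

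A participant whose magrolimab/placebo was reduced would not vanish either. Delay comes first, so that participant should appear in the delay summary with reasons and in the delay listing. The event would be in the by-arm table of treatment-related Grade 3 or higher events for each drug, and the doses would be in the dose-intensity categories and the administration listing.

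Most of this stands, and it limits the point. A reader might infer that holds of magrolimab/placebo are not shown at all. The documents do not support that, because 4.2.1 counts delay for each drug with reasons. If adverse event is a recorded reason, the number delayed for toxicity will be available. A reader might also infer that delay is the usual response to magrolimab/placebo toxicity. Protocol 6.7.1.2 permits delay conditionally and stresses keeping to schedule. Nor do the documents show that the burden of the added agent is hidden, since the events themselves and the discontinuations are tabulated by arm.

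The reply does not remove the blank reduction row. Rarity is an expectation, and without a count the report cannot show whether it held. Piecing reductions together from listings is possible, but it is not a prespecified comparison between arms.

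**Conclusion.** The point holds in a narrow form. Magrolimab/placebo reductions, which the protocol allows, have no count, no TEAE table and no dedicated listing. TEAEs leading to delay or interruption have a listing but no by-arm SOC/PT table, so the events behind holds of magrolimab/placebo are not tabulated.

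The practical weight is small. This is a matter of safety reporting; no endpoint, estimate, alpha or sample size depends on it, and reductions are expected to be few. The gap is firmest for reductions. For delays it is one of detail, because the counts and reasons are already planned.

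Two assumptions apply. The 4.2.1 summary is taken to be by arm, although the sentence does not say so. The eCRF is not among the documents, so whether it records reduction of magrolimab/placebo as an action taken for an adverse event is unknown.

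**What to change.** - In SAP 4.2.1, summarize dose reduction or delay for each drug, with reasons, by treatment group.
- In SAP 7.1.6.1, widen the reduction category, in both the table and the listing, to any study drug and each study drug, matching the discontinuation category.
- In SAP 7.1.6.1, keep the listing for delay or interruption and add a by-arm SOC/PT table of those TEAEs for each study drug.

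The cost is a few words and two extra tables, with probably small counts in the reduction table. The events leading to delay must be identified for the planned listing in any case. For reductions, first confirm that the eCRF captures the action taken for magrolimab/placebo. SAP Section 1 says the plan is finalized before data finalization for the second interim analysis, so the tables can be prespecified if that point has not passed. After it, Section 1 requires the change to be documented in the clinical study report. No dose or treatment rule is altered.

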4.2.2. Relative Dose Intensity

Relative dose intensity is the percentage of the total amount of study drug administered relative to the total amount of study drug expected to be administered during a subject's actual on-treatment period based on the study drug regimen.

For magrolimab/placebo:

The relative dose intensity is the percentage of the total amount of study drug administered relative to the total amount of study drug expected to be administered, expressed as a percentage using the following formula:

Relative dose intensity (%) =
$$\left(\frac{\text{Cumulative Dosage Received (in mg/kg)}}{\text{Magrolimab/Placebo Dosage to be Administered}}\right) \times 100$$

on Treatment (in mg/kg)

Cumulative dosage (mg/kg) received for each subject is defined as the sum of all delivered dosages (mg/kg) of all infusions the subject received.

,

Magrolimab/placebo dosage to be administered on treatment (mg/kg) for each subject is defined as the total amount of magrolimab/placebo the subject was expected to receive during the subject's treatment period.

For azacitidine:

Relative dose intensity (%) =
$$\left(\frac{\text{Total Amount of Azacitidine Administered}}{\text{Azacitidine Expected to be Administered on Treatment}}\right) x 100$$

For each study drug, descriptive statistics for the relative dose intensity with the number and percentage of patients belonging to relative dose intensity categories (eg, <75%, ≥75 to <90%, $\geq90\%$) will be provided by treatment group for the Safety Analysis Set.

A by-subject listing of each study drug administration will be provided by treatment group, subject ID number (in ascending order) and visit (in chronological order).

4.3. **Protocol Deviations**

Patients who did not meet the eligibility criteria for study entry, but enrolled in the study will be summarized. The summary will present the number and percentage of patients who did not meet at least 1 eligibility criterion and the number of patients who did not meet specific criteria by treatment group based on the ITT Analysis Set. A by-subject listing will be provided for those patients who did not meet at least 1 eligibility (inclusion or exclusion) criterion. The listing will present the eligibility criterion (or criteria if more than 1 deviation) that patients did not meet and related comments, if collected.

Protocol deviations occurring after patients entered the study are documented during routine monitoring. The number and percentage of patients with important protocol deviations by deviation reason (eg, nonadherence to study drug, violation of select inclusion/exclusion criteria) will be summarized by treatment group for the ITT Analysis Set. A by-subject listing will be provided for those patients with important protocol deviation.

4.4. Assessment of COVID-19 Impact

This study was ongoing during the novel coronavirus (COVID-19) pandemic which has an impact on the study conduct. Some subjects were unable to attend onsite visits due to shelter in place guidelines, site closures, or other reasons. This section describes how special situations due to COVID-19 will be handled in the analysis.

4.4.1. Study Drug Discontinuation Due to COVID-19

A summary of reasons for discontinuing study drug due to COVID-19 will be provided by treatment group and overall, similar to the summary described in the subject enrollment and disposition section (see Section 4.1).

A by-subject listing of reasons for study drug discontinuation due to COVID-19 will be provided if applicable.

4.4.2. Protocol Deviations Due to COVID-19

A summary of important protocol deviations due to COVID-19 will be provided, similar to the summary described in the protocol deviations section (Section 4.3).

The number and percentage of subjects with non-important protocol deviations related to COVID-19 will be summarized by treatment group.

A by-subject listing will be provided for subjects with important protocol deviations related to COVID-19 if applicable.

4.4.3. Missed and Virtual Visits due to COVID-19

An overall summary of the number and percentage of subjects with at least 1 missed scheduled or virtual visits due to COVID-19 will be provided by treatment group and overall. The denominator for the percentage calculation will be the total number of subjects in the safety population for that column.

4.4.4. Adverse Events Due to COVID-19

A by-subject listing of AEs of COVID-19 will be provided if applicable.

5. **BASELINE CHARACTERISTICS**

5.1. Demographics and Baseline Characteristics

Subject demographic variables (ie, age, sex at birth, race, ethnicity, geographic region) and baseline characteristics (body weight [in kg], height [in cm], body mass index [BMI; in kg/m²], Body Surface Area [BSA; in m²]) will be summarized by treatment group and overall using descriptive statistics for continuous variables and using number and percentage of patients for categorical variables. The summary of demographic data will be provided for the ITT Analysis Set.

A by-subject demographic listing, including the informed consent date, will be provided by treatment group and subject ID number.

5.2. Other Baseline Characteristics

Other baseline characteristics include but are not limited to: ECOG, BM blast, Cytogenetic Risk Status, and TP53 mutational status. These baseline characteristics will be summarized by treatment group and overall using descriptive statistics for continuous variables and using number and percentage of patients for categorical variables. The summary of these baseline characteristics will be provided for the ITT Analysis Set. No formal statistical testing is planned.

A by-subject listing of other baseline characteristics will be provided.

5.3. Medical History

Medical history will be collected at screening for disease-specific and general conditions (ie, conditions not specific to the disease being studied).

MDS Diagnosis history will be summarized by treatment group and overall, by the number and percentage of patients with each prepopulated categories including but not limited to: IPSS-R, WHO Classification of MDS, Therapy-related MDS, RBC Transfusion Independence. The summary will be provided for the ITT Analysis Set. Time since diagnosis (months) will be calculated by (date of randomization – date of diagnosis) / 30.4375. Time since diagnosis will be summarized using summary statistics for a continuous variable. No formal statistical testing is planned. A by-subject listing of disease-specific medical history will be provided. In deriving the time since disease diagnosis, all partial dates of diagnosis and last regimen will be identified, and the partial dates will be imputed as follows:

- If day and month are missing but year is available, then the imputed day and month will be 01 Jan.
- If day is missing but the month and year are available, then the imputed day will be the first day of the month.
- Partial date will not be imputed if the year is missing.

6. EFFICACY ANALYSES

6.1. Primary Efficacy Endpoints

6.1.1. Definition of Primary Efficacy Endpoints

The two primary efficacy endpoints of this study are CR rate and OS.

CR Rate: The CR rate is the proportion of patients who reach morphologic CR (morphological blast of \leq 5% and recovery of ANC, platelets, and hemoglobin from complete blood counts as well as peripheral blast) based on Investigator-assessed IWG 2006 MDS criteria {Cheson 2006} on or prior to initiation of any new anticancer therapy, including SCT.

Overall Survival: The OS is measured from the date of randomization to the date of death from any cause. Those who are not observed to die during the study will be censored at their last known alive date.

The date of the last known alive will be determined by selecting the last available visit date across all datasets.

For participants who come off the study, study staff may use public records (eg, public health records) to obtain information about survival status where allowable by local regulation.

Every attempt will be made to ensure that complete death dates are recorded. In those rare instances where complete death dates are not recorded, the following algorithm will be used:

- If day is missing but the month and year are available, then the imputed date will be the 1st day of the month or the last known alive date + 1, whichever is later.
- If day and month are missing but year is available, then the imputed date will be 01Jan of that year or the last known alive date + 1, whichever is later.

When the date of initiation of a new anticancer therapy other than the study treatment or the date of SCT is incomplete or missing, the following algorithm will be followed:

- If the day is missing but the month and year are available, then the imputed day will be the first day of the month or the day of last dose + 1 if the month and year of new anti-cancer therapy and the month and year of last dose are the same.
- If day and month are missing but year is available, then the imputed day and month will be 01Jan or the date of last dose + 1 if the year of new anti-cancer therapy and the year of last dose are the same.

